12.2 INSTITUTIONAL REVIEW BOARD

The protocol and study materials have been submitted to a single, centralized IRB (Advarra) for review. IRB approval and waivers of consent and HIPAA authorization applicable to the pilot study and the Zelen design were obtained in September 2020 for the protocol and trial.

Protocol modifications made for the full trial will be approved by the IRB before any human subjects activities are initiated for the trial. Amendments require IRB review and approval before changes are implemented at either site.

12.3 INFORMED CONSENT PROCESS

See Section 6.3 for a description of the modified, verbal consent process for intervention arm patients. NCMs will only outreach to the 50% of subjects randomly selected for the offer of the CC intervention, and the consent process will focus only on the offer of CC.

The study information sheet has been written with the aim of using plain language, minimizing the cognitive burden, and separating clearly what are study activities vs. clinical care (e.g., risks section).

12.3.1 PARTIAL DISCLOSURE OF STUDY RELATED ACTIVIES

During recruitment and consent for the MI-CARE program, patients randomized to be offered the intervention are told that the program is for patients with stress or low mood, who take or used to take opioids.

The oral consent process does not fully disclose all study-related activities.

During recruitment of patients randomized to be offered the intervention, the NCMs do not disclose that:

- (1) People are only eligible for the trial if they have an indication that they have OUD in their EHR in the past year;
- (2) Their health data will be included in study outcome analyses, or that they may not opt out of this data being included in trial analyses, (to preserve the integrity of the Zelen design);
- (3) That we are testing an intervention designed to engage non-treatment seeing patients with OUD into evidence-based medication treatment for OUD; and
- (4) That the outcomes of the trial are only partly focused on depressive symptoms; the primary outcome is days of medication treatment for OUD.

This partial disclosure of study related activities is acceptable because:

- 1) The trial and trial analyses pose no more than minimal risk to intervention arm participants;
- Trial analyses rely solely on secondary data sources (other studies using only secondary data for analyses are exempt);
- 3) The waiver does not adversely affect the rights or welfare of subjects. Patients are informed we are studying the offer of extra support from a NCM, in addition to usual care. They are free to decline participation in CC without impacting their welfare or right to health care services;
- 4) The important question about whether proactive outreach to patients with OUD and significant mental health symptoms can increase access to evidence-based OUD treatment and potentially improve important clinical care like suicide, overdose and death—could not practicably be carried out without the waiver of documentation and alteration of consent; and
- 5) As appropriate over time, NCMs will share information about OUD treatment options as well as provide added information about the goals of the study (e.g., increasing access to evidence-based treatment for OUD).

6) In addition, as the trial progresses, the NCM will elicit patient perspectives on how the program might be improved, including sharing further details about the goals of the study in these debriefs.

12.3.2 SPECIAL CONSIDERATION, RESEARCH INVOLVING PRISONERS: 45 CFR 46 SUBPART C

This study does not target prisoners as subjects; however, we expect that patients with OUD and cooccurring mental health conditional will be at increased risk of justice-involvement compared to the general population. As such, it is possible that intervention arm patients could become incarcerated, placed under house arrest, or put on parole as deferred prosecution while in the 12-month CC program. We believe that this study meets the requirements of 45 CFS 46.306 because:

- The CC program has the intent and a reasonable probability of improving the health and/or well-being of participant by supporting treatment for OUD, depression and other common conditions (e.g., other substance use, anxiety, pain).
- Any possible advantages to the patients in the CC program are not so great as to bias or impair the participant's decision making while in a limited choice environment (e.g., standard, evidence-based treatments; subjects are not compensated; CC is not in person but virtual);
- The risks involved in the research are commensurate with risks that would be accepted by non-justice-involved participants (primarily, breach of confidentiality for this minimal-risk study);
- Procedures for the selection of subjects is based on clinical criteria and is in no way related to justice-involvement;
- The study information sheet and consent script used plain language; and,
- Patients who become prisoners while in CC will be clearly informed in advance that participation in the study will have no direct effect on his or her parole.

Taking into account that only a handful of CC patients are expected become justice-involved, we do not expect that the IRB would find a need for follow-up examination or care of participants after the end of their participation. The intervention continues to be provided within the IUH and KPWA health systems. Participants are informed of this during the consent process. We believe that the standards of care, clinical documentation (e.g., EHR) requirements, and clinical supervision by health system managers, clinical experts and study team members provide adequate provision for such examination or care.

13 DATA HANDLING AND RECORD KEEPING

13.1 QUALITY AND ACQUISITION OF AUTOMATED DATA FOR ANALYSES

All data needed to implement the SAP for the trial will be collected from automated data sources both internal (e.g., EHRs) and external to the health systems (e.g., insurance claims or HIE, PMP). The study will conduct routine checks of data collected from electronic health systems and look for data anomalies (e.g., missing, out of range). These data sources will be:

	KPWA	IUH	SOURCE
Electronic health system records	\boxtimes	\boxtimes	EHR, data warehouses
External hospital and emergency dept use		\boxtimes	Indiana health information exchange
External hospital and emergency dept use	\boxtimes		Insurance claims
Buprenorphine and other opioid data			State Prescription Monitoring Programs, claims, EHR records
Buprenorphine and other opioid data			Pharmacy data, Insurance claims
Buprenorphine and other opioid data			Indiana health information exchange
Death records	\boxtimes	\boxtimes	State departments of health

Research staff at KPWA and IUH may need to conduct targeted manual chart reviews to understand data for specific patients with data anomalies (e.g., duplicate orders, two hospital stays on the same day, hospital discharge date precedes the admit date). In addition, focused structured chart abstraction will be conducted for all study enrollees to validate quality (and potentially supplement) automated EHR data regarding patient clinical and demographic characteristics and receipt of study-relevant clinical services at the time of study enrollment. Such information may serve as important predictors of study outcomes. While conducting these chart reviews, our abstractors will also review the electronic health record for any known patient death data (e.g., date of death, cause of death, etc.). Although we hope to receive the most complete validated death data from Washington state via our pre-existing KPWA institutional data sharing agreement, we may not be given approval to send the state data to the Indiana honest broker site where we'll be conducting our trial analyses. We will transfer the most complete death data we are able to gather from the EHR chart abstractions, pending availability of the state death data and approval to transfer it to Indiana.

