3.2.3.1 FORMATIVE EVALUATION OUTCOMES

Formative evaluation includes both qualitative and quantitative components to support future implementation.

Qualitative elements of formative evaluation will identify barriers and facilitators to implementing the intervention in this pragmatic trial. Weekly debriefs of NCMs, with research staff observing and taking field notes on all meetings, will be used to surface important issues. These will be used to populate a virtual white board with sticky notes and then code barriers and facilitators into domains including: the external environment, such as changes in the opioid epidemic, or waivers needed to prescribe buprenorphine; the MI-CARE intervention, such as issues with engagement of patients and primary care providers and their teams, or changes in standard care; patients and the health systems, such as characteristics of eligible patients and primary care teams and others in the health systems; and implementation and sustainment infrastructure, related to how the intervention is integrated into each organization in a sustainable manner, as in building EHR tools for NCM use. Our NCM team will also conduct chart reviews of all MI-CARE enrollees (usual care, invited to CC but not consented and consented, to find information that is not readily identifiable through EHR data pull, specifically qualitative information that contextualizes our study variables (see Chart Abstraction form). In addition, the team will conduct qualitative interviews with all staff delivering the MI-CARE intervention (NCMs) and OBAT nurses supporting treatment to better understand their experiences with the training and support on the MI-CARE intervention at both sites. See Supplement 4 for additional information outlining this process.

Quantitative elements of formative evaluation will be based on RE-AIM model (Reach, Effectiveness, Adoption, Implementation fidelity and Maintenance). Reach, adoption and implementation fidelity will be evaluated. (Effectiveness is evaluated as above in main aims, and Maintenance after the trial is beyond the scope of this study).

• Reach of the Intervention. We will evaluate the overall reach at the patient level - namely, demographic and clinical characteristics of those consenting for treatment and engaging in care contrasted to those invited but failing to consent/engage in care. Further, we will evaluate uptake of core component elements at the patient level including: NCM engagement, use of

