3.3.1.2 MAJOR ACUTE ADVERSE HEALTH EVENTS

A composite of any major adverse event over 12 months of follow-up, which includes: opioid overdose, other drug overdose, suicide attempt or other self-harm, hospitalizations (opioid and non-opioid), or death (from secondary data sources).

Rationale: This outcome assesses whether improved depressive symptoms and OUD and pain management has patient safety benefits.

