3.3.1.4 OTHER SECONDARY EXPLORATORY OUTCOMES

Due to the heterogeneity of the sample and the expected heterogeneity of benefits across different subsamples (e.g., heroin use vs prescribed opioids for pain as route to OUD), a number of secondary outcomes will be used to describe outcomes. Each individual component of secondary outcomes (e.g., buprenorphine for pain, suicide attempt, opioid overdose) will also be evaluated independently.

- Descriptive measures related to OUD will be assessed in both arms, including engagement in primary care for OUD and/or pain; other treatments for OUD (e.g., naltrexone, methadone from outpatient treatment programs (OTPs) as well as behavioral treatments inside or outside the health system such as counseling for SUD or addiction treatment programs, or inpatient addiction treatment), secondary prevention outcomes (e.g., urine drug screening including fentanyl, naloxone prescription for OD prevention, Hepatitis C virus (HCV) and HIV screening, absence of non-buprenorphine opioid and benzodiazepine prescribing); chances in treatment for OUD (e.g., initiation of new buprenorphine for OUD); days of buprenorphine pain treatment (e.g., Belbuca, Butrans, etc.); and other treatments for pain (e.g., specialty treatments for pain, other pain treatments, and new buprenorphine for pain).
- Depression measures assessed during follow-up (both arms) will include measures of
 measurement-based care, medication treatment, and counseling or behavioral treatments for
 depression of other mental health disorders (e.g., no follow-up PHQ score documented in the
 EHR; number of documented PHQs in follow-up, new or change in antidepressant medication or
 increase in antidepressant dose in 12 months follow-up; counseling for depression, inpatient
 psychiatric treatment, and suicidal thoughts on PHQ-9).
- Risk factors for adverse or improved outcomes will include urine drug screens with "unexpected" outcomes (e.g., lack of prescribed buprenorphine, opioids not prescribed, methamphetamine and other drugs, cannabis); prescribed opioids aside from buprenorphine; chronic prescription opioids at doses exceeding CDC established safety threshold of ≥ 50 morphine milligram equivalents per day (MED); prescription opioid use above lowest level safety threshold (≥ 20 MED)^{34, 35}; prescribed benzodiazepines.

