6.6.4 LOSS OF CONTACT FOLLOWING CONSENT

The NCM may lose contact with a patient who previously consented for many reasons (e.g., relapse, death, housing or financial instability, loss of phone access). During CC engagement, the NCM may ask the patient for additional contact person(s) or means through which to communicate with the patient, should contact be lost. If the NCM is concerned for the patient's safety (e.g., recent overdose or relapse), the emergency contact in the EHR may be contacted, per care standards.

The NCM will also utilize approaches described in Section 6.6.2 for patients never able to be reached (e.g., call attempts spread across days and times, voice messages, mail and/or web portal communications, EHR review) and may also message a study- or health system-verified email address or cell number, in keeping with the health system's standard practices.

The NCM will continue outreach in a tapered manner. Patients remain eligible for NCM support over the full 12-month period, should they choose to reach out.

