10.3 ADVERSE EVENTS (AE) / SERIOUS ADVERSE EVENTS (SAE) AND REPORTING

We aim for harm reports to rely on data sources collected uniformly across study arms and not to include AEs and SAEs observed differentially among patients in the intervention arm. Many events, such as suicide, overdose, hospitalization and/or death may be documented in patients' electronic medical records (EMR) by NCMs (e.g., learned due to NCM outreach after missed appointments). Due to the pragmatic study design, such SAEs will not be observed in the control arm and use of EMR data may introduce bias. We therefore restrict harm monitoring to adverse events that lead to acute care in emergency departments or hospitalization, documentation of which are less likely to be biased by the intervention.

We will report self-harm (e.g., suicide attempt) and opioid or other drug overdose(s), that result in ED visits or hospitalizations (psychiatric and non-psychiatric), and all-cause mortality (by manner of death), in the intervention arm compared to usual care arms. We will include any intentional poisoning (overdose) as a suicide attempt as well. We will report the number, percent, and rate of these serious adverse events (SAEs) in each harm report for the DSMB to review. Formal sequential tests to compare SAEs between arms will not be conducted because the number and rate of events are expected to be too small to be able to detect statistically significant differences. Blinding will be in place to assure that the study team is not looking at outcome data across treatment arms during the trial.

There is a lag between when an event may occur and when the event information is recorded and available in the data sources utilized. To allow sufficient time for data capture, datasets used to generate the DSMB harm reports will be administratively censored according to a plan documented in an approved DSMB report template (up to a 3-month lag). We will be evaluating trial outcomes using a 6-month lag to allow us to maximal time to obtain completed claims and state death records (the latter of which have variable and unpredictable lags up to 24 months in Washington).

10.3.1 REPORTING OF INTERVENTION GROUP DEATHS AND UNEXPECTED AND RELATED SAES LEARNED OF INCIDENTALLY BY NCM

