Any unrelated deaths, and unexpected and related SAEs, that NCMs learn of will be summarized for the DSMB with each report and reported to the NIMH DSMB liaison and program official no later than 5 business days after a principal investigator learns of the death (per NIMH reporting policy). Unexpected and related SAEs will be reported within 10 business days to the same NIMH staff. The patient's care team will also be notified via the EHR.

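### For KPWA deaths, section 13.1 falls back on chart-abstracted records that section 10.3 treats as open to bias between arms, and adds no safeguard

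*Protocol*

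**What the plan says.** The table in Protocol section 13.1 gives state departments of health as the source of death records for both KPWA and Indiana University Health (IUH). The text below it says that KPWA hopes to obtain Washington's validated records under an existing agreement, but may not be allowed to send them to the Indiana site where the trial is analysed. In that case: "We will transfer the most complete death data we are able to gather from the EHR chart abstractions, pending availability of the state death data". Charts of all enrollees in both arms are to be abstracted.

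Section 10.3 discusses the same source when it sets up harm reporting. It says that "death may be documented in patients' electronic medical records (EMR) by NCMs", for example after outreach for missed appointments, and continues: "Due to the pragmatic study design, such SAEs will not be observed in the control arm and use of EMR data may introduce bias".

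Death is a component of the major acute adverse health event composite (3.3.1.2). Section 3.3.1.4 adds that each individual component of the secondary outcomes "will also be evaluated independently".

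**The concern.** Section 10.3 identifies a route by which deaths enter the chart in one arm only. Section 13.1 then names the chart as the fallback for KPWA deaths in the trial data. It does not mention that concern, require the origin of a death to be recorded, or separate NCM entries from others.

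If the fallback is used, KPWA deaths may be recorded more completely in the intervention arm than in usual care. With equal true mortality this looks like harm; with a true reduction it hides part of the benefit. The outcome at stake is death on its own. Section 7.2 names a reduction in death among the hoped-for benefits, so readers will look at that comparison even though it is exploratory.

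**Working it through.** The protocol gives no mortality rate, no chart-capture rate for deaths and no site split. There is no stated figure to reproduce, so the check is textual, followed by the form of the bias and a timing calculation.

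**1. Who can write a death into the chart.** In both arms, the usual clinical staff can. In the intervention arm, NCMs can as well:
- 6.6.4 lets them ask consented patients for further contact people.
- 10.3 describes outreach after missed appointments.
- 10.3.1 says of deaths and related events learned by NCMs that the patient's "care team will also be notified via the EHR".

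NCMs have no contact with usual-care patients.

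**2. Whether abstracting every chart equalises this.** It does not. The procedure is the same in both arms, but the content being abstracted is not.

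**3. Form of the bias at KPWA.** Let c be the share of usual-care deaths that reach the chart, and δ the extra share that reaches it in the intervention arm only because of NCM contact.

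- Recorded risk ratio = true risk ratio × (c + δ)/c = true risk ratio × (1 + δ/c).

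Since δ ≥ 0, the factor is at least 1. The protocol gives neither c nor δ, so the size cannot be computed. Complete state records at IUH would dilute the factor in a pooled estimate.

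**4. Why dropping NCM entries is not a cure.** Let d be the share of deaths that other staff would have recorded but an NCM entered first. Removing all NCM entries leaves capture of c − d in the intervention arm.

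- Recorded risk ratio = true risk ratio × (1 − d/c).

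This factor is at most 1 and falsely favours the intervention. The two versions err in opposite directions, so both need to be shown.

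**5. Effect on the composite.** Section 8.3.3 analyses time to the first event, and 3.3.1.2 counts every hospitalization. An extra recorded death changes a patient's event status only if no earlier qualifying event occurred, so the composite should move little.

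**6. Whether the fallback could reach the final analysis.** Section 10.3 puts the Washington lag at up to 24 months, against a 6-month lag for trial outcomes. Section 13.1.1 plans the analysis for April–May 2024, and 7.3 says funding ends in May 2024. An interim source could therefore become the one analysed.

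**7. Cost of cutting death follow-up where the state file is complete.** Assume uniform accrual over 12 months (8.1 expects enrolment over that period) and data closing at month 31 (Synopsis).

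- 24-month lag: the file is complete to month 31 − 24 = 7. Mean follow-up per patient is (7²/2)/12 = 24.5/12 = 2.04 of 12 months, or 17%.
- 12-month lag: the file is complete to month 19. Entrants in months 0–7 keep 12 months each (7 × 12 = 84). Entrants in months 7–12 keep (12 + 7)/2 = 9.5 on average (5 × 9.5 = 47.5). The mean is (84 + 47.5)/12 = 10.96 months, or 91%.

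At the longest lag, truncation would discard most KPWA death follow-up. It would also leave the components of the composite with unequal follow-up.

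**The case against.** The best defence has four parts.

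- **Scope of 10.3.** Its preference for sources uniform across arms is written for harm reports, while 13.1 concerns trial data. That is correct, and this is a tension rather than a broken rule. The reason given in 10.3, however, concerns how events reach the record, and that does not depend on the report's purpose.
- **Transfer is not analysis.** Section 13.1 commits only to sending the data. Source flags and sensitivity analyses may be in the statistical analysis plan, which is not at hand. This is fair as far as it goes. But the transferred file is what will be analysed, and a source variable not captured at abstraction may be hard to recover later.
- **State records are already preferred**, and the fallback is disclosed and conditional on outside approval. This stands: the fallback may never be used.
- **NCM knowledge may add little.** Section 6.6.2 has NCMs learn of some deaths by re-reading the chart, which adds nothing to it. Section 8.4 also expects KPWA records and claims to capture most adverse-outcome data, though it does not speak of death specifically. Both points argue for a small effect.

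A reader might also infer that the abstractors are the nurses who treat intervention patients, because 3.2.3.1 says "Our NCM team will also conduct chart reviews of all MI-CARE enrollees". The protocol does not say that these are the abstractors of 13.1, and the point does not need it.

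**Conclusion.** The point holds as a minor one. Under the fallback, the stand-alone death comparison at KPWA would rest on a source that the protocol itself regards as open to bias between arms. The likely direction is more recorded deaths in the intervention arm. This assumes that NCM contact adds at least some deaths to the chart that would otherwise be missed.

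The size cannot be derived, because capture, mortality and site split are all unstated. A reader might infer a large spurious mortality signal or a threat to the main results. The protocol supports neither. Aims 1 and 2 are not defined by death, so the effect there is nil, and for the composite it is probably negligible. Nor does the point extend to the non-fatal components: serious opioid-related events (3.3.1.3) are already tied to emergency department or hospital care or to overdose, and definitions for the others may be in the analysis plan.

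**What to change.** Amend section 13.1 as follows.

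1. Record the source of every death: state record, chart entry not made by an NCM, or NCM entry.
2. Make state records the main source for the between-arm death comparison at both sites. If the only obstacle is transfer to Indiana, analyse the KPWA stratum at KPWA, which 13.3 already makes the data coordinating center, and pool the site-specific estimates. This is consistent with the Cox model stratified by health system in 8.3.3.
3. If Washington records are still incomplete because of lag at the analysis cut-off, state the cut-off. Label any result that uses chart-abstracted KPWA deaths as a sensitivity analysis subject to differential ascertainment, show it with and without NCM-sourced entries, and update it when the state file is complete.

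Death follow-up need not be truncated as a rule, given the loss shown above.

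The cost is a few sentences, one variable per death and possibly a small local analysis. The real downside is a death result that may come later or be less complete: local analysis removes the transfer problem but not the lag, and funding ends in May 2024.
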